9.0 Consent Process

Individuals that have previously consented to be contacted about future research studies will be contacted and phone screened to determine preliminary eligibility. They will be scheduled for their screening visit, which will take place at the Center for Biomedical Imaging in the BSL suite. Informed consent will be reviewed with the potential participant by a member of the key personnel on this proposal. The consent will be signed by the participant as well as one of the Key Personnel on the proposal. A copy of the consent will be given to the subject and the original placed in the research record. All records will be stored in locked departmental files. Section 301(d) of the Public Health Service Act of November 4, 1988 also protects a layer of protection for the privacy of health information for individuals that engage in federally funded medical research.

10.0 Study Design / Methods

Multidisciplinary Team. We have assembled diverse talents to develop translational approaches to TMS treatment development for opiate dependence. Our team has extensive experience in: 1) TMS ([name]), 2) NIH trials in chronic lower back pain ([name], [name]), 3) pain management ([name]), 4) neuroimaging ([name]), and 5) statistical modeling ([name], [name]). In addition to providing critical effect size data for a planned R01, this grant will provide an opportunity for several MUSC trainees in the DART Resident research program ([name]), and a NIDA T32 ([name] [name]) to get hands-on training with neuroimaging, TMS, and opiate dependent individuals. [name] will serve as a scientific advisor and meet regularly with the team to provide insight on outcomes and patient recruitment.

Overview. The proposed study will be the first to employ a randomized, double-blind, sham-controlled design to parametrically evaluate the longitudinal effects of 16 days of rTMS to the DLPFC (Aim 1) or the MPFC (Aim 2) on self-reported pain and the brain's response to pain. This will be done in a cohort of patients recruited from MUSC clinics and the outer community with chronic lower back pain. Participants will be randomized to receive TMS to the DLPFC, MPFC, or sham (50% at each site), using a Latin square randomization. Resting state connectivity will be collected at each MRI scanning session.. Quantitative Pain Testing will be collected 12 times. MRI data will be collected 3 times: before the 1st visit of TMS, before the 12th visit of TMS, and before the 16th visit of TMS.

Table 1. Study Design. Aim 1&2 will be conducted in parallel.

^primary goal: evaluate 2 TMS strategies as tools to decrease acute pain and brain reactivity to pain.

^secondary goal: durability

Screening	Group Assignment	Induction Phase				Maintenance Phase				Follow Up Phase							
		Week 1	2	3	4	5	6	7	8	9	10	11	12	13	14	15	16
	TMS Sessions	XXX	XXX	XXX	XXX	X	X	X	X								
	Clinical Assessments	XXX	XXX	XXX	XXX	X	X	X	X	X	X	X	X	X	X	X	
	Quantitative Urinalysis	X	X	X	X	X	X	X	X	X	X	X	X	X	X	X	
	Quantitative Pain Testing	X	X	X	X	X	X	X	X	X	X	X	X	X	X	X	
	Neuroimaging				X				X								

Participants. We will enroll 48 men and women 18-75 years old with CLBP that have a history of current prescription opioid use (>3 months) for the treatment of pain. Participants will be recruited through the community along with MUSC clinics. Patients that have previously agreed to be contacted for research and have current chronic pain will be referred to the study. Our prior history with targeted enrollment (See Significance) indicates this is feasible within 20 months, leading to full completion by 22 months. **Exclusion criteria:** Typical MRI and TMS exclusionary criteria, including metal above the neck or implanted in the body, use of prescription medications that lower seizure threshold, a history of seizures or traumatic brain injury, pregnancy or trying to become pregnant, current substance use or dependence (other than opioids and nicotine), history of seizure disorder, and claustrophobia. Participants will provide written informed consent following explanation of the study. **Sample size estimate:** A power estimate for Aim 1 and 2 was prepared using an original fMRI dataset previously collected in our laboratory (8). In this experiment, 18 healthy controls performed the same fMRI pain paradigm as the present study before and after a single session of 10 Hz rTMS. Mean parameter estimates for the “heat pain vs. rest” condition were extracted from several *a priori* regions of interest. These data yielded an effect size which ranged from 0.70 (thalamus) to 1.08 (insula) (n=15 yields 80% power using a two-sided p<0.05). Allowing for a 10% dropout rate after the screening visit, and up to a 20% dropout rate at the end of the Treatment phase (Week 4), as well as a 10% data loss rate for MRI (Aim 2) due to individuals with excessive head motion in the MRI scanner, screening 58 individuals should lead to complete data from 48 individuals (16 real DLPFC, 16 real MPFC, 16 sham (50% at each site)). Randomization will be handled by the MUSC data coordination center of the Biostatistical Unit ([name], biostatistician) and a Latin Square design with replacement will be used to ensure even enrollment across groups with replacement.

General Methods

Screening Visit – Consent. Participants will receive a series of assessments designed to evaluate opioid dependence, psychiatric conditions, chronic pain and mood. These include the MINI International Neuropsychiatric Interview (46), Brief Pain Inventory (47), Timeline Followback (48), Becks Depression Inventory II (49), State-Trait Anxiety Inventory (50), the Pittsburgh Sleep Quality Index (PSQI), the Barratt Impulsiveness Scale (BIS), and Profile of Mood States (51). Data will be collected using REDCap™, and entered directly into the online portal to ensure security and prevent data loss.

Intervention –●MRI Visits 1-3. Following enrollment, participants will meet the study personnel for Assessment & MRI Scanning (details below). The procedures at MRI Visit 1 will be repeated at MRI Visit 2 (after 12 days of rTMS), and at MRI Visit 3 (after 16 days of rTMS). **●rTMS Treatment sessions:** After the Screening visit, patients will be randomized to receive 16 days of real or sham rTMS treatment. Based on prior studies in our laboratory that have applied 10 days of TMS to various clinical populations,

[figure not shown]

Figure 3. TMS stimulation sites, derived from EEG 10-20 landmarks.

we expect 16 sessions of TMS treatments (3 days per week for 4 weeks, followed by 1 day a week for 4 weeks) will take 8 weeks, allotting time for a weekend (as is conventional in this field), holidays and/or one missed appointment. In the event that an individual drops out before completing the 16 TMS sessions, the number of sessions received will be a covariate in the analyses. Cortical Targeting: After the MRI scans participants will be escorted into the Brain Stimulation room (30 feet away) where scalp localization will be performed for the TMS procedure. The Cartesian position of the coil (X,Y,Z) will be determined by standardized positions from the EEG 10-20 system: 1) F3 (left DLPFC stimulation (Aim 1)), 2) FP1 (MPFC stimulation (Aim 2)). The angular position of the coil (pitch, yaw, roll) will be determined by the individual's cortical geography beneath FP1 and F3 using the individual's T1 scan for guidance. The locations and coil orientation will be indicated on a nylon cap which will be worn during the TMS sessions. We will then determine the participant's resting motor threshold (RMT, the minimal amount of stimulation required over the hand area of the primary motor cortex to induce contraction of the APB muscle of the hand 50% of the time) via the standardized PEST procedure (106, 107). During each TMS session, we will take a non-identifiable photo of the participants' forehead (eyes covered with an index card) to ensure the coil is correctly placed each time they return to the lab. This will be cross-checked with the neuronavigation data.

Strategy 1: iTBS to the left dlPFC. For intermittent theta burst stimulation (Aim 1), participants will receive 20 trains of stimulation over the dlPFC (middle frontal gyrus) (F3) (each train: 3 pulse bursts presented at 5Hz, 15 pulses/sec for 2 sec, 8 sec rest, 200 pulses/train; 110% RMT, MagPro; 600 pulses total) using a figure 8 coil (Coil Cool-B65 A/P).

Strategy 2: cTBS to the vmPFC. For continuous theta burst stimulation (Aim 2), participants will receive 1 train of stimulation over the left frontal pole (FP1) (each train: 3 pulse bursts presented at 5Hz, 15 pulses/sec for 40 sec, 600 pulses/train, 110% RMT, MagPro; 600 pulses total) using a figure 8 coil (Coil Cool-B65 A/P). This protocol has been shown to attenuate the mPFC and striatum in cocaine dependent individuals in the past (61-63) and has been more effective than 1200 or 1800 pulses of cTBS in attenuating depression (The time between the end of the TBS procedures and the beginning of the behavioral assessments, as well as the scalp-to-cortex distance (which effects the actual TMS dose given to the cortex) will be compiled and used as covariates in subsequent analyses.

ACTIVE SHAM system. The MagVenture MagPro system has an integrated, active sham which passes current through two surface electrodes placed on the scalp. The electrodes will be placed on the left frontalis muscle for all sessions. A patient ID card will randomize participants to receive either real or sham stimulation. This system maintains blinding by a gyroscope in the coil which indicates to the clinical staff whether the coil should be rotated up or down for this participant once the card is entered into the machine. One side of the coil is active, the other is sham. The integrity of the double-blind procedure will be assessed by asking the patients and study personnel rate their confidence regarding whether they thought they received real or sham (scale 1-10).

•**Assessments:** The primary dependent measures will be extracted from the Quantitative Sensory Testing for pain thresholds. Other assessments include: Brief Pain Inventory (BPI), the pain craving form, and subjective pain rating scales, delivered before and after TMS. Participants will also complete the Beck Depression Inventory (BDI-II), the Profile of Mood States (POMS), the Pittsburgh Sleep Quality Index (PSQI), the State-Trait Anxiety Inventory (STAI), and Barratt Impulsiveness Scale (BIS), which assesses anxiety and depression measures. Though these are not primary outcomes, the results will be used in post-hoc analyses of the data. All surveys will be filled out by the patient on tablet computers (Apple iPad/Microsoft Surface) and data entry will be done directly via Redcap Software. •**MRI scanning:** The MRI scanning session will last 30 minutes and will contain: 1) a high resolution anatomical image (T1-weighted MPRAGE (TR 1.9 sec, TE 2.26 ms, 2x GRAPPA, 1 mm isotropic)), 2) resting state functional connectivity (TA 7 minutes, voxel size: 2.5 x 2.5 x 2.5, TR = 2.6 s, TE = 25 ms, flip angle = 60°, FOV = 224 mm x 224 mm, matrix size = 64 x 64), **For each of the above strategies (Active rTMS or Active Sham) we will explore a**

series of SubAims designed to quantify the effects of rTMS on subjective pain, quantitative sensory testing, and brain reactivity to pain.

SubAim 1: Evaluating Pain using Clinical Assessments Quantitative Sensory Testing (QST). Using the Medoc ATS thermal stimulator (Medoc Ltd Advanced Medical Systems, Ramat Yishai, Israel), 3 primary outputs will be compiled for each individual via the method of limits (54): sensory threshold, pain threshold, tolerance threshold. The thermode will be attached to the right forearm, and when the procedure begins it will begin heating from room temperature (32°C) at 0.2°C per second. Participants will indicate when they first detect the temperature change (sensory threshold), when it becomes painful (pain threshold), and when they can no longer tolerate the stimuli (tolerance threshold). When participants indicate tolerance, the operator will initiate rapid (>8°C per second) cooling. For safety, the thermode will be unable to exceed 51° and will initiate rapid cooling at that point. QST will be performed at two timepoints for each visit – prior to the initial MRI session and after the second MRI session. **Pain Questionnaire.** In order to evaluate current levels of pain, we will ask participants to rate their current level of pain and discomfort (scale, 0 through 10), each time the participant comes in (Table 1). On days where the individual receives rTMS, they will fill out this assessment before and after each session. **Pain and Craving Questionnaire:** In addition to the Pain Questionnaire above, participants will also rate their urge to use a pain reliever (Scale 0 – 10) and the amount they would be willing to pay for a pain reliever (In US Dollars). This questionnaire will be used at the same time during each intervention visit as the Pain Questionnaire (Table 2).

SubAim 2: Evaluating Pain using Neuroimaging Data At baseline we expect that people with chronic pain will have elevated activations in the Pain Network. This will be analyzed through the resting state connectivity network. Following sham stimulation, we do not anticipate a significant reduction of this response. Based on prior studies by our group in non-opiate dependent individuals, following LTP-like stimulation of the DLPFC, we expect a significant amplification of the DLPFC (% BOLD signal change), and a reduction of the Pain Network (dACC, anterior insula) reflecting the increased influence of executive processes. MPFC TMS however will likely not have as large of an effect on ECN engagement during the instruction to Control the pain.

Data Analysis Plan.

A. Quantitative Sensory Testing. The QST pain assessment produces 3 output variables: sensory threshold, pain threshold, tolerance threshold (all expressed in degrees Celsius). The hypothesis will be tested using a within-subject repeated measures design (time x treatment) wherein time is the repeated variable and Real or Sham TMS is the grouping variable. Given that the purpose of this pilot study is to develop effect sizes for a subsequent R01, we will derive least-squares means effect sizes of this strategy on these thresholds. Secondary analyses will evaluate the relationship between QST levels and the neural response to pain, as well as the relationship between QST values and evoked cortical responses. Integrating these measures together will provide a more complete picture of how cortical activity is able to modulate the pain response.

B. Questionnaires and Evaluations. The Opiate Pain inventory produces 4 output variables of interest: level of discomfort, level of pain, urge to use opiates, amount willing to pay for an opiate. The hypotheses for the Aims will be tested using a within-subject repeated measures design (time x treatment) wherein time is the repeated variable and Real or Sham TMS is the grouping variable. Given that the purpose of this pilot study is to develop effect sizes for a subsequent R01, we will derive least-squares means effect sizes of our research strategy on these 4 variables, to determine the unique contributions of this intervention.

C. Neuroimaging Data (Aim 2): Immediately following acquisition, functional structural data will be uploaded to a secure data server and converted to NIfTI format. All preprocessing and analyses will be

performed using Statistical Parametric Mapping 12 (SPM12) in Matlab 2013 (Mathworks). Functional data will be corrected for magnetic field inhomogeneity and realigned (rigid-body, minimizing least squares differences) to the first image in the time series (Realign: Estimate and Unwarp). Non-linear deformations required for standard space normalization will be derived from each participant's anatomical image via a unified segmentation approach (Segment). After the mean realigned and unwarped functional image is coregistered to the skull stripped anatomical image (Coreg: Estimate) forward deformations (subject space to MNI standard space) will be applied (Normalise: Write). Finally, the data will be smoothed by an 8 mm full width half maximum Gaussian smoothing kernel (Smooth). Within-subject and between-group modeling. Data will be analyzed at the subject level using multivariate pattern analysis (Wager et al 2013 "An fMRI-Based Neurologic Signature of Physical Pain" new England Journal of Medicine). The six motion parameters (translations and rotations) will be included in the design matrices as covariates to account for non-task signal. The hot and warm blocks of thermal stimulus, as well as rating events, will be separately modeled in a boxcar fashion. Resting State Connectivity will be measured to compare MRI scan 1 to scan 2 – immediately after the treatment. MRI scan 3 will also be compared to these scans to see if there is a sustainable reduction in pain activity between these networks. Additionally factor analysis will be used to investigate the durability of the effects of each strategy on functional connectivity in each of the 3 Core networks (SN, ECN, DMN) using factor analysis longitudinally. **Covariates:** As an exploratory analysis we will also quantify the impact of several covariates which have previously been documented to affect the brain response to pain and pain thresholds (sex, Becks Depression Inventory score, length of time using chronic opiates). Although all participants will have taken their daily dose of opiates, which has a stable pharmacokinetic profile, we will also consider time since last dose.

Expected (and alternative) Outcomes:

A. Quantitative Pain Testing. Based on our pilot data, we expect an interaction between treatment (Real DLPFC or MPFC TMS vs. Sham) and time (Before vs. After rTMS) on the painfulness QST measure but no effect on sensory or tolerance levels. Alternative outcomes: It is possible that individuals will experience a small level of acute pain relief from their normal regimen of medication. We will be collecting information on opiate dose and timing at each visit to be used as potential covariates. Further, there is the possibility that pain tolerance will rise, possibly also reflecting improvements in executive function.

B. Qualitative Pain Assessment. We expect reductions in pain and discomfort when comparing active vs sham. However, based on prior data in opiate dependent individuals, we expect the effect size of DLPFC rTMS in to improve measures of Control but not measures of mood, whereas MPFC will have a larger effect on mood.

C. Neuroimaging. At baseline we expect that there will be elevated activations in the Pain Network in individuals with chronic pain. Following sham stimulation, we do not anticipate a significant reduction of this response. Based on prior studies by our group in non-opiate dependent individuals, following LTP-like stimulation of the DLPFC, we expect a significant amplification of the DLPFC (% BOLD signal change), and a reduction of the Pain Network (dACC, anterior insula) reflecting the increased influence of executive processes. MPFC TMS however will likely not have as large of an effect on ECN engagement during the instruction to Control the pain.

Alternative outcomes: Though pilot data suggest that a single treatment will acutely reduce self-reported pain, it is possible that the neural circuits in opiate dependent individuals do not have the same 'plasticity potential' as in controls. The results of the baseline cortical modulation assessment of pain (instruction to "control" the pain) will help resolve this alternative outcome. If we fail to replicate prior work showing DLPFC activation, this could reflect executive deficits (58), suggesting that the MPFC TMS will be more efficacious.

Exploratory Analysis: We will evaluate if there are rate-dependent effects between baseline SN connectivity with the ECN and DMN and the efficacy of each TMS strategy on subjective pain. Data will be analyzed by using multivariate pattern analysis (MVPA) (2014). While the primary outcomes will be MRI V1 vs V2, we will also examine the relative ‘durability’ of the effects on pain by comparing the MRI data at the 1 month follow up between and within groups with factor analysis. **Integration of Brain based and Behavioral Based Outcomes with Gender and other Demographic Variables:** Finally, we will compare the relative efficacy of these two types of TMS using the behavioral and neuroimaging measures. Specifically, we will determine the effect sizes for DLPFC and MPFC (relative to sham) stimulation on reducing the 1) the neural and 2) behavioral responses to pain, as well as 3) changes in clinical assessment metrics (see Approach). We will investigate the role of baseline cortical responsiveness on the pain response, as well as how changes in that evoked response are related to changes in both pain and craving measures. This will be specifically addressed as a factor of gender as well, given that there are established differences in sensitivity to pain and prevalence of opiate dependence between men and women.

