1.0 Objectives / Specific Aims

Effective control of chronic pain is a top priority in the United States, as approximately 10% of adults have severe chronic pain – most of which is chronic lower back pain (CLBP). However, despite the advances in neuroscience over the past 20 years, we still largely treat chronic pain with opiate narcotics, much as was done in the Civil War. In addition to their high abuse liability and dependence potential (1), only 30–40% of chronic pain patients declare they receive satisfactory (>50%) relief from their pain through pharmacological treatment (Attal et al., 2006). In these patients a common clinical practice is to escalate the dose of opiates as tolerance develops – which unfortunately has contributed to escalation in opiate overdose deaths (2), a resurgence of intravenous heroin use, and \$55 billion in societal costs (3). **Consequently there is a critical need for new, treatments that can treat pain and reduce reliance on opiates in individuals with chronic pain.**

The goal of this R21 proposal is to evaluate 2 novel non-invasive brain stimulation strategies to mitigate pain and the brain's response to pain in CLBP patients that are currently taking chronic opiates, or that are seeking an alternative treatment for pain. Transcranial Magnetic Stimulation (TMS), can induce long term potentiation (LTP-like) and long term depression (LTD-like) effects on brain activity in a frequency dependent manner. Our group has previously demonstrated that LTP-like TMS to the dorsolateral prefrontal cortex (DLPFC, a node in the Executive Control Network (ECN)) can decrease perceived pain and corresponding BOLD signal in the ‘Pain Network’ (7, 8, 10-12). The Pain Network is an expansion of the Salience Network (SN; insula, dorsal anterior cingulate) which includes the thalamus and somatosensory cortex(4-6). The analgesic effects of DLPFC TMS can be blocked by naloxone – suggesting that the analgesic effects of LTP-like DLPFC TMS are opiate mediated. Additionally, DLPFC TMS delivered postoperatively leads to less patient administered morphine use (PCA-pump) in the hospital and less opiate use in the outpatient setting (9). **These data all suggest that LTP-like DLPFC TMS is a promising candidate for treating pain (Strategy 1, Aim 1).**

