An alternative strategy is to apply LTD-like stimulation to the medial prefrontal cortex (LTD-like mPFC rTMS (Strategy 2, Aim 2). This strategy is based on our understanding of functional neural architecture, wherein the SN is modulated by 2 other core networks: the executive control network (ECN) and the default mode network (DMN). As stated above, it is possible to attenuate activity in the SN through LTP-like TMS to the DLPFC, a node in the ECN. It is also possible to attenuate the SN through LTD-like TMS to the ventral medial prefrontal cortex (a node in the DMN). **The proposed study will be the first to employ a randomized, double-blind, sham-controlled design to parametrically evaluate the longitudinal effects of 16 days of rTMS to the DLPFC (Aim 1) or the MPFC (Aim 2) on self-reported pain and the brain's response to pain. This will be done in a cohort of patients recruited from the community as well as MUSC clinics with chronic lower back pain that have not been able to find adequate pain relief, whether or not they are using prescription opiates for 3 or more months.** Participants will be randomized to receive rTMS to the DLPFC (iTBS), MPFC (cTBS), or sham (50% at each site), using a Latin square randomization. Resting state connectivity will be collected 3 times: before the 1st day of TMS, after the 12th day of TMS, and before the 16th day of TMS (the last day administered).

Aim 1. Evaluate DLPFC rTMS as a tool to dampen pain and the engagement of the Pain Network. Hypothesis 1: DLPFC TMS will attenuate the baseline brain response to pain (Pain Network activity) and increase activity in the ECN when the patient is given instructions to ‘control’ the pain.

Aim 2. Evaluate MPFC rTMS as a tool to dampen pain and the engagement of the Pain Network. Hypothesis 1: MPFC TMS will also attenuate the baseline brain response to pain (Pain Network activity) but will not effect the ECN or SN when the patient is given instructions to ‘control’ the pain.

(Exploratory Aim): We will evaluate if there are rate-dependent effects between baseline SN connectivity with the ECN and DMN and the efficacy of each TMS strategy on subjective pain. Data will be analyzed by using multivariate pattern analysis (MVPA) (2014). While the primary outcomes will be MRI V1 vs V2, we will also examine the relative ‘durability’ of the effects on pain by comparing the MRI data at the end of all TMS visits between and within groups with factor analysis.

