5.0 Inclusion and Exclusion Criteria/ Study Population

Participants. We will enroll 48 men and women 18-75 years old with CLBP. These individuals can also have a history of current prescription opioid use (>3 months) for the treatment of pain. Participants will be recruited through MUSC clinics as well as the outer community. Patients that have previously agreed to be contacted for research will be referred to the study or contacted via telephone. The risks of MRI and TMS to the unborn fetus are not well understood. Therefore, to be included, females must not be pregnant

as determined by a urine pregnancy test and must be utilizing reliable birth control during the course of the study.

Inclusion Criteria:

1. Age 18-75 (to maximize participation)
2. Can currently be using prescription opiates
3. Able to read and understand questionnaires and informed consent.
4. Is not at elevated risk of seizure (i.e., does not have a history of seizures, is not currently prescribed medications known to lower seizure threshold)
5. Does not have metal objects in the head/neck.
6. Does not have a history of traumatic brain injury, including a head injury that resulted in hospitalization, loss of consciousness for more than 10 minutes, or having ever been informed that they have an epidural, subdural, or subarachnoid hemorrhage.
7. Does not have a history of claustrophobia leading to significant clinical anxiety symptoms.

Exclusion Criteria:

1. Any psychoactive illicit substance use (except marijuana and nicotine) within the last 30 days by self-report and urine drug screen.
2. Meets DSM-V criteria for current axis I disorders of obsessive-compulsive disorder, bipolar affective disorder, schizophrenia, dissociate disorders, eating disorders, and any other psychotic disorder or organic mental disorder.
3. Has current suicidal ideation or homicidal ideation.
4. Has the need for maintenance or acute treatment with any psychoactive medication including anti-seizure medications and medications for ADHD.
5. Females of childbearing potential who are pregnant (by urine HCG), nursing, or who are not using a reliable form of birth control.
6. Has current charges pending for a violent crime (not including DUI related offenses).
7. Does not have a stable living situation.
8. Suffers from chronic migraines.

Inclusion of Women and Minorities

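### Prescription opioid use is required, optional and assumed universal in different sections, and the opioid covariates offered are either undefined for non-users or measured after randomisation

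*Combined protocol and SAP*

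**What the plan says.** All of this is current text in the one combined document.

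- **Required.** Section 10.0, Participants, enrols 48 people with chronic low back pain "that have a history of current prescription opioid use (>3 months) for the treatment of pain".
- **Optional.** Section 5.0 says "These individuals can also have a history of current prescription opioid use (>3 months) for the treatment of pain", and its inclusion criterion 2 reads "Can currently be using prescription opiates". Section 1.0 recruits patients "whether or not they are using prescription opiates for 3 or more months"; section 2.0 says the same.
- **Assumed universal.** The Covariates text of section 10.0 begins a sentence "Although all participants will have taken their daily dose of opiates", and goes on to consider time since the last dose. Part B of the Data Analysis Plan names two of its four outcomes in terms of opiates.
- **Main models.** Parts A and B of the Data Analysis Plan fit time, treatment (real or sham) and their interaction. Neither contains an opioid term. No stratification of the randomisation by opioid use is stated.
- **Opioid covariates.** Duration of opiate use is listed for an exploratory analysis. Under Expected (and alternative) Outcomes, part A, the plan adds: "We will be collecting information on opiate dose and timing at each visit to be used as potential covariates".
- **Why opioid use might matter.** Section 1.0 reports that naloxone blocks the analgesic effect of DLPFC stimulation, "suggesting that the analgesic effects of LTP-like DLPFC TMS are opiate mediated", and that postoperative DLPFC stimulation was followed by lower opiate use. Section 2.0 doubts whether the relevant circuits are as plastic in chronic opiate users as in healthy controls.

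**The concern.** The trial exists to supply effect sizes for a later grant application. An effect size needs a defined population, and here a reader cannot tell whether it will describe opioid users or a mixture in unknown proportion.

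Two analysis problems follow. An opioid covariate written for a cohort of users may have no value for a non-user, and the plan gives no coding rule. And a dose recorded during treatment is not a baseline characteristic. If stimulation reduces opiate use, holding dose fixed removes a part of what stimulation did, and the comparison is no longer protected by randomisation.

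**Working it through.** The documents give no share of opioid users and no calculation on this point, so there is no figure of the plan's own to reproduce. Steps 1 to 3 rest on the text alone. Steps 4 to 6 say what does and does not follow numerically.

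**1. Population.**

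| Place | Non-users enrolled? |
|---|---|
| 10.0, Participants | No |
| 1.0, 2.0, 5.0 (text and criterion 2) | Yes |
| 10.0, Covariates | Assumed absent |

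The second row contradicts the other two.

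**2. Covariates for a non-user.** Duration of opiate use can sensibly be set to 0. Time since last dose cannot: there is no last dose. Taking 30-70% non-users (assumption), 0.30 x 48 = 14.4 and 0.70 x 48 = 33.6, so about 14-34 of 48 participants would have no value. This touches only models that use that covariate, which the plan merely says it will consider.

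**3. Dose and timing at each visit.** Both are recorded after randomisation. Section 1.0 cites less opiate use after DLPFC stimulation. On that evidence, dose may lie between treatment and pain, and a contrast adjusted for it is no longer the total effect of assignment.

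**4. Does leaving opioid use out of the main model bias it?** Let U = 1 for a user and 0 otherwise, let b be a constant user/non-user difference in level, and let g be a difference between them in change over time. With complete before and after data:

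- Change for one participant = time effect + treatment effect on change + gU. The term bU is in both measurements and cancels.
- Error in the time-by-treatment estimate from imbalance = g x (user share in arm 1 - user share in arm 2).

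So b contributes nothing, and adding U as a main effect alone leaves the estimate unchanged. Only g matters. For a gap of 4 users between arms of 16, the error is g x 4/16 = 0.25g. The documents give no value for g.

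**5. How likely is such a gap?** With X and Y independent Binomial(16, q), P(|X - Y| >= 4) is 17.5% at q = 0.30 or 0.70 and 21.5% at q = 0.50. The range for q is an assumption, and the figure is context only.

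**6. Could effect modification by opioid use be tested?** Take two arms of 16, user share q in each, and outcome SD 1. The standard error of the interaction is sqrt(2/(16q) + 2/(16(1-q))), with 28 degrees of freedom.

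- q = 0.50: sqrt(2/8 + 2/8) = 0.71.
- q = 0.30 or 0.70: sqrt(2/4.8 + 2/11.2) = 0.77.

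If the interaction is as large as the whole planning effect, two-sided 5% power is 14-16% at 0.70 and 27-31% at 1.08. Those effect sizes come from imaging in healthy controls and serve only as a scale. An estimate with its interval is all that this sample can support.

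**The case against.** **The opioid covariates are peripheral.** Duration of use is exploratory, time since last dose is to be considered, and visit-level dose and timing are only potential covariates, meant to deal with relief from usual medication. This stands as a limit on severity: the main models exclude nobody, and nothing commits the main analysis to post-randomisation adjustment. But nothing rules it out either.

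**Imbalance is already provided for.** The quality assurance plan in section 13.0 will examine baseline comparability in case adjustment is needed. This stands in part. It names no variable, leaves the decision until the data are seen, and does not touch the undefined covariate or on-study dose.

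**The within-subject design protects the contrast.** For a stable difference in level this is right (step 4). A reader might infer that omitting opioid use biases the planned contrast whenever users and non-users have different pain thresholds, or that one yes/no covariate would sharpen it. The documents do not support either, because the planned test is on change.

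**Opiate mediation does not mean prescription use alters response.** This also stands. The statement concerns DLPFC stimulation only, and the title of the cited naloxone study refers to endogenous opioids. A reader might take it as showing that prescription users respond differently, or extend it to MPFC stimulation; the text does neither. The doubt in section 2.0 about plasticity in chronic users is the better reason to look for effect modification, and it is a doubt, not a finding.

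**Conclusion.** The concern holds as a defect of population definition and covariate choice. The contradiction is certain from the text, and the documents do not settle which eligibility rule was intended. Time since last dose is undefined for any non-user, affecting perhaps 14-34 of 48 (30-70% non-users assumed) in exploratory models only. Adjusting for visit-level dose or timing can remove part of the treatment effect; how much cannot be sized from the documents.

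No numerical bias in the main time-by-treatment result is shown. It would need users and non-users to change differently over time and the arms to be unbalanced on use. A gap of 4 or more users between two arms has a chance of 17.5-21.5% under the assumed shares, but the difference in change is unknown. The point should be dealt with before analysis because it decides whom the effect sizes describe.

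**What to change.** 1. State one population in sections 1.0, 2.0, 5.0 and 10.0, including the covariate text and the outcome names in part B of the Data Analysis Plan. The choice is for the investigators.
2. Do not adjust treatment contrasts for on-study opiate dose or timing. Report both as outcomes by arm. Use only pre-randomisation opioid variables as covariates.
3. If non-users remain eligible:
   - Prespecify baseline opioid use (yes/no) together with its interaction with time in the repeated-measures models, or as a covariate in a baseline-adjusted model of change. A main effect alone is not enough.
   - Set duration of use to 0 for non-users, and confine any analysis of time since last dose to users, labelled as such.
   - Show arm by opioid use by time as an exploratory estimate with its confidence interval.
4. If only users are eligible, the yes/no covariate has no variation and is omitted; items 1 and 2 still apply.

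The cost is wording, plus one degree of freedom in a change model or two in a before/after repeated-measures model (more if time has many categories). Screening precedes randomisation and already includes an assessment of opioid dependence and the Timeline Followback, so baseline use should need little or no extra data collection.
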